## 2. STUDY OBJECTIVES

### **Main objective:**

To implement and evaluate the effectiveness of a multi-component intervention with evidence-based activities, to reduce the gaps in hypertension care and control at population level

### **Secondary objectives:**

- To improve the quality of hypertension care provided by the public primary health care services in the Commune 2-Santa Cruz.
- To increase detection of hypertension by blood pressure screening outside the clinical settings and contribute to the public awareness on the importance of healthy behaviour and self-care to prevent cardiovascular diseases.
- To carry out a process evaluation of the intervention and its implementation fidelity in order to assess to which degree the components of the intervention were implemented as intended and how the intervention actually influenced hypertension control outcomes.

### 3. STUDY DESIGN

A multi-component intervention for the improvement of hypertension care and control in individuals aged 35 years or older will be implemented and evaluated. The components of the intervention integrate activities related to: A) Health services organization, B) Training of clinical staff, and C) Patients and community engagement. The effectiveness of the intervention in reducing the gaps in hypertension care and control will be evaluated in a quasi-experimental, controlled before-after trial, with an intervention arm (a commune of Medellin) where the intervention is deployed, and a control arm (another commune of Medellin, with similar characteristics) where routine care is implemented. As baseline, the results of the population-based cross-sectional study "Gaps in hypertension care and control in Medellin, Colombia: cross-sectional survey in two Communes", Version 2.0, dated 26-AUG-2018 approved by the UZA Ethics committee on 15/10/2018, will be used. Twenty-four months after the start of the intervention, a population-based cross-sectional survey with similar methodology as the baseline survey will be carried out in the intervention and control commune. The main outcomes (magnitude of the gaps in hypertension care and control) will be assessed with difference in difference measures (endline-baseline changes in the intervention minus endline-baseline changes in the control commune). The total duration of the study will be 32 months, of which 24 allocated to the implementation of the intervention. Implementation fidelity will be evaluated in order to assess to which degree the components of the intervention were implemented as intended and how the intervention actually influenced hypertension control outcomes.

The proposed research is part of a concerted effort within the Latin American Network for Multidisciplinary Research on Chronic Diseases, which is co-coordinated by the principal investigator of the study, [name]. This is a regional network for multidisciplinary research on the prevention and control of chronic non-communicable diseases in Latin America, comprised of partner institutions and supported by ITM (Unit of General Epidemiology and Disease Control). Parallel studies, following comparable research protocols and applying data collection tools with a common core part, are being conducted in Havana-Cuba and Quito-Ecuador.

The study is part of the PhD research of [name] entitled “Addressing gaps in hypertension care and control in Medellin, Colombia: formative research, multi component quasi-experimental intervention”.

## 4. METHODS

### 4.1 Study Setting, Population and Sampling Strategy

#### 4.1.1 Study setting

Medellin is the capital of the department of Antioquia, in Colombia. It has a population of 2,5 million people and 16 Communes. The intervention will be implemented in the “Santa Cruz” Commune, located in the northeast side of Medellin. It has 11 neighbourhoods, an area of 2.2 Km^2, a total population of 113.024 inhabitants (53% women and 47% men) in 2018. In Santa Cruz, Metrosalud counts with a Hospital Unit and two health centers. In Metrosalud diagnosed hypertensive patients are enrolled in the Cardiovascular Risk Program (CVRP) that foresees periodic consultations for the management of their hypertension, called cardiovascular risk consultations. Different community organizations, represented by community leaders, have been supporting Metrosalud’s work in community- and health-related activities for many years. The Commune 6-“Doce de Octubre” has been selected as control area. It is located in the northwest side of Medellin, has 12 neighbourhoods, an area of 3.8 km^2, and a total 2018 population of 193.657 inhabitants (53% women and 47% men). The commune was chosen purposively, especially due to its socio-economic similarities with the Santa Cruz Commune and after discussion with the Director General of Metrosalud, who approved the selection of these two areas.

#### 4.1.2 Study population, Sampling, Sample Size and Power

The study communes are chosen purposively according to the following inclusion criteria: urban setting; low and/or middle-income population; typical functioning of the national health system; commitment of the main actors in health care provision in the area to develop improvement programmes based on research results.

All health structures and their catchment population aged 35 years or older will be involved in the study.

For the endline survey, the same methodology applied for the aforementioned baseline survey will be used. Expecting a baseline hypertension control gap of 45%, a sample of 280 hypertensive individuals 35 years or older is required to estimate a 10% difference in the magnitude of the control gap in the intervention vs the control area at endline, with power 0.75 and alfa 0.10. Given a 40% prevalence of hypertension (see 4.1.4 for definitions) in individuals aged 35 years or older, screening around 700 individuals 35 years or older in each Commune, will allow to find the needed number of hypertensive individuals. This is increased to 1150 individuals, assuming a percentage of non-response of 10% and a design effect of 1.5, given the sampling strategy outlined below. From a sampling frame containing the addresses of all homes of the Communes, provided by the Planning Office of the Municipality, a stratified one-stage cluster sampling will be implemented in order to obtain a representative sample of the population aged 35 years or older living in the selected Communes. Considering that in households there are on average 1.5 individuals 35 years old or older, 765 households will be included in each Commune. In each Commune, clusters of 15 contiguous households will be defined with the help of maps and 51 clusters will be selected by randomly sampling each neighbourhood of the Commune. The number of randomly selected clusters in each neighbourhood will be proportional to the neighbourhood size (weights assigned to each neighbourhood according to its total number of households). The module for complex samples of the Statistical Package for Social Sciences (SPSS) V.24 (SPSS Inc., Chicago, IL, USA) will be used. Door to door visits to every single household of each selected cluster will be made by a group of trained surveyors. All identified eligible consenting individuals aged 35 years or older will be interviewed.

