The effectiveness of the intervention in reducing the gaps in hypertension care and control will be evaluated in a quasi-experimental, controlled before-after trial, with an intervention arm (a commune of Medellin) where the intervention is deployed and a control arm (another commune of Medellin, with similar socio-economic characteristics) where routine care is implemented. As baseline, the results of the population-based cross-sectional study "Gaps in hypertension care and control in Medellin, Colombia: cross-sectional survey in two Communes", Version 2.0, dated 26-AUG-2018, approved by the UZA Ethics committee on 15/10/2018, will be used. Two years after the start of the intervention, a repeat survey using the same methodology as in the baseline will be carried out in the two communes. The main outcomes (gaps in hypertension care and control) will be assessed with difference in difference measures (endline-baseline changes in the intervention minus endline-baseline changes in the control commune).

The study aims at contributing to the improvement of hypertension care and control in Colombia and may inspire and inform with scientific evidence other initiatives for better chronic care in LMIC, especially in Latin America.

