### 4.3 Data Analysis

#### 4.3.1 Quantitative Data Analysis

The main outcomes (dependent variables) of the analysis at population level will be the gaps in hypertension care and control (Table 1). Uni, bi- and multivariate analysis will be performed. For the main outcomes, difference in difference measures will be calculated (endline-baseline changes in the intervention minus endline-baseline changes in the control commune). Where relevant, we will stratify on affiliation to Subsidized or Contributory insurance schemes. Logistic regression models adjusting for potential confounding variables will be fitted. Unadjusted and adjusted Odds Ratios (ORs) and their 95%CI will be calculated.

The indicators for monitoring the implementation and measuring the results and effects of the intervention at health service level are listed in the following table (Table 3). They have been elaborated also taking into account the standardized performance indicators proposed by the SHTP and Global Hearts project (2). The indicators will be measured both in the intervention and in the control area, at baseline, at regular intervals during implementation, and at endline.

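### The only stated power (0.75) is for an endline-only contrast; the main measure is a difference-in-differences, with power about 0.52 if the baseline matches the endline in size and is independent of it

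*Combined protocol and SAP*

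**What the plan says.** Section 4.1.2 gives the sizing, which starts from "Expecting a baseline hypertension control gap of 45%, a sample of 280 hypertensive individuals". The purpose given for a sample of this size is "to estimate a 10% difference in the magnitude of the control gap in the intervention vs the control area at endline, with power 0.75"; the planning alpha is 0.10. The 280 is per commune, since 280 / 0.40 prevalence = 700 people to be screened in each. This is raised to 1,150 for a design effect of 1.5 and 10% non-response.

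The declared effect measure is a different one. Section 3: "The main outcomes (magnitude of the gaps in hypertension care and control) will be assessed with difference in difference measures". The Synopsis says the same ("The main outcomes (gaps in hypertension care and control) will be assessed with difference in difference measures"), as does section 4.3.1 ("For the main outcomes, difference in difference measures will be calculated"). In each place this is the endline-minus-baseline change in the intervention commune minus the same change in the control commune.

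On the baseline, section 4.1.2 says only "For the endline survey, the same methodology applied for the aforementioned baseline survey will be used". Its sample size is not given. For the endline sampling, "51 clusters will be selected by randomly sampling each neighbourhood of the Commune"; the section does not say whether these could be the baseline clusters.

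**The concern.** A difference-in-differences has four estimated proportions in it and an endline contrast has two. Unless the baseline is very large or strongly correlated with the endline, the extra sampling error lowers power, so the 0.75 does not carry over to the main measure.

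The measure cannot be treated as secondary. The communes were chosen purposively and not randomised, so an endline comparison alone cannot remove differences that existed before the intervention. The plan's only power figure therefore belongs to a comparison that is not its main one. A reader who meets a null difference-in-differences and looks up the stated power would conclude that a 10-point effect had probably been ruled out. Under the plainest reading of the baseline, a true effect of that size would be missed about half the time.

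**Working it through.** **Inputs from section 4.1.2:** control gap 45%; 10-point difference, so 35% in the intervention commune at endline; 280 hypertensives per commune; alpha 0.10; power 0.75; design effect 1.5; non-response 10%; prevalence 40%. Sidedness is not stated. **Assumed, because the documents do not give them:** the baseline number of hypertensives per commune, and the baseline–endline correlation.

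**1. Reproduce 280.** The variance terms are 0.45 × 0.55 = 0.2475 and 0.35 × 0.65 = 0.2275. Two-sided alpha 0.10 gives z = 1.645, and power 0.75 gives z = 0.674.
- Unpooled: (0.2475 + 0.2275) × (1.645 + 0.674)² / 0.10² = 255.5
- Pooled variance under the null: 257.4
- Pooled with continuity correction: 277

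So 280 is an endline-only size, two-sided. One-sided alpha 0.10 would need only about 182. At 280, without continuity correction, endline power is 0.78 (0.68 at alpha 0.05).

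**2. Is there slack in the 1,150?** 1,150 × 0.9 × 0.40 = 414 hypertensives, and 414 / 1.5 = 276 effective. The inflation only restores the 280.

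**3. Difference-in-differences.** With nb effective hypertensives per commune at baseline and independent surveys:

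SE² = 2 × 0.2475 / nb + (0.2475 + 0.2275) / 280; power = Φ(0.10 / SE − z).

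For nb = 280, SE² = 0.001768 + 0.001696 = 0.003464 and SE = 0.0589. Power = Φ(1.699 − 1.645) = 0.52.

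| Baseline per commune (effective) | SE | Power, alpha 0.10 | Power, alpha 0.05 | Detectable at power 0.75 (alpha 0.10 / 0.05) |
|---|---|---|---|---|
| 140 | 0.0723 | 0.40 | 0.28 | 16.6 / 18.8 points |
| 280 | 0.0589 | 0.52 | 0.40 | 13.6 / 15.4 points |
| 560 | 0.0508 | 0.63 | 0.50 | 11.7 / 13.3 points |
| 1,000 | 0.0468 | 0.69 | 0.57 | – |

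The detectable effects use the variance at the rate that each effect implies. Reaching 0.75 at alpha 0.10 would take a baseline of about 3,050 per commune.

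**4. Correlation between surveys (baseline 280).** A correlation of 0.2 gives SE 0.0526 and power 0.60 / 0.48 (alpha 0.10 / 0.05). Power 0.75 at alpha 0.10 needs a correlation of about 0.46. If the same clusters were revisited with different people, the correlation is bounded: 414 / 51 = 8.1 hypertensives per cluster; a design effect of 1.5 implies an intracluster correlation of 0.5 / 7.1 = 0.070; the most that shared clusters can contribute is 8.1 × 0.070 / 1.5 = 0.38, which gives power 0.70 / 0.58. A simulation with 51 clusters of 8 (20,000 runs) agreed: 0.51 / 0.38 with redrawn clusters, and 0.68 / 0.57 with the same clusters and perfect cluster-level correlation.

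**5. Which control gap is the 45%?** Table 1 defines the gap over all hypertensives. On the 2016 one-commune figures in section 1.2 that is 0.367 + 0.633 × 0.41 = 0.627, about 63%; the aware-only gap is 41%. Starting from 63% gives power 0.53 / 0.40, so little changes. If aware-only is meant, the numbers shrink: 414 × 0.633 = 262 aware, 5.1 per cluster, design effect 1 + 4.1 × 0.070 = 1.29, 262 / 1.29 = 203 effective. SE is then 0.068 and power 0.43 / 0.31.

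**The case against.** The strongest objection is that the baseline has its own approved protocol, which the reader of this one does not have. The baseline sample size, and perhaps a power statement for the paired design, may be there, so 0.52 rests on an assumed size. That is fair about the number, and 0.52 should be read as conditional. It does not remove the mismatch: this protocol builds its main measure on that baseline, and the only power it quotes is for something else. Power also stays below 0.75 for every baseline size from 140 to 1,000.

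Second, the text reads most naturally as a fresh draw of clusters, so the correlation scenarios may be idle. If so, independence is the right case and 0.52 is the relevant figure. The scenarios matter only because the plan does not settle the question. Re-interviewing the same people could raise power further, but nothing in the plan describes that.

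Third, 280 matches 0.75 only with continuity correction, while 0.52 comes from an uncorrected formula under which the endline power is 0.78. This stands. Put on a basis where the endline contrast has exactly 0.75 (255.5 effective per cell, unpooled), the difference-in-differences has SE 0.0616 and power 0.49. The conclusion is the same, but the revised text should use one method for both.

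Fourth, there is one commune per arm, so any of these figures covers sampling error only and not commune-specific change over time. That also stands, and it means 0.52 is if anything generous.

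Finally, no estimate is biased, no sum in section 4.1.2 is wrong, and a null result ought to be judged by its interval. All true. But section 4.3.1 plans intervals explicitly only for the odds ratios, so the stated power is what a reader would reach for.

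**Conclusion.** The concern holds. It is a mismatch between what was sized and what will be estimated; the sizing itself is sound for the endline contrast. With 280 effective hypertensives per commune in each of two independent surveys, power for a 10-point difference-in-differences is about 0.52 at two-sided alpha 0.10 and 0.40 at 0.05. The true effect would then be missed 48% of the time at alpha 0.10, or from 37% (baseline 560) to 60% (baseline 140). The mismatch is certain from the text; the exact power depends on the baseline size and on any overlap between surveys, neither of which is stated.

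Two smaller points need clarifying in the same place. Planning uses alpha 0.10, whereas section 4.3.1 says "Unadjusted and adjusted Odds Ratios (ORs) and their 95%CI will be calculated" and gives no level for the difference-in-differences. And the 45% is not identified as the Table 1 gap or the aware-only gap, which matters only if it is the latter.

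**What to change.** In section 4.1.2:

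- State that 280 per commune gives power 0.75 for the endline contrast only.
- Add the power or detectable effect for the difference-in-differences, computed by the same method from the actual baseline number of hypertensives per commune after the design effect.
- Say whether endline clusters are redrawn or revisited, and whether anyone is re-interviewed.
- State whether the 45% is the Table 1 control gap or the aware-only gap. If aware-only, compute power on the aware subgroup.

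If the baseline has the same effective size and clusters are redrawn, the added text could read: *With 280 effective hypertensives per commune per survey, power for a 10-point difference-in-differences in the control gap is about 0.52 (two-sided alpha 0.10, no continuity correction; on this basis the endline contrast has power 0.78). The effect detectable with power 0.75 is about 13.6 points. These figures allow for sampling error only, not for commune-specific change over time.*

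In section 4.3.1, state one error level for the difference-in-differences and use it in both planning and reporting. At alpha 0.05 the figures become about 0.40 and 15.4 points.

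The cost is a wording change and looking up the baseline sample size. No extra enrolment is asked for. The stated power for the main measure becomes less favourable.

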#### 4.1.3 Inclusion and Exclusion Criteria

- In order to be eligible for the endline survey, study participants must meet the following criteria:

- » Aged 35 years or older

- » Permanent inhabitant of the selected Commune
- » Willing and able to provide written informed consent.

- In order to be eligible for in-depth interviews and non-participant observation (qualitative component):
  - » Adult patient aged 35 years or older or health staff of Metrosalud.
  - » Active participant of any component of the intervention or subject of any intervention activity.
  - » Willing and able to provide written informed consent.

Potential participants meeting any of the following criteria will not be enrolled in the study:

- » Mental disability or unable to answer the questionnaire.

#### 4.1.4 Definitions

Hypertensive individual (operational definition for survey): self-report of previously diagnosed hypertension or without previous diagnosis but presenting an average blood pressure (BP) measurement higher than 140/90 mmHg(11;16).

Presumptive hypertensive individual: no self-report of previously diagnosed hypertension but presenting an average BP measurement higher than 140/90 mmHg.

Controlled hypertensive individual: self-report of previously diagnosed hypertension and an average BP less than 140/90 mm Hg for patients between 35 and 59 years old or diabetics and 150/90 mm Hg for patients aged 60 years or older (17).

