## 1.2 Rationale

In Colombia, the death rate from CVD in 2014 was 146.9 per 100.000 population. In this country, 30% of all deaths and 16.3% of Years of Life Lost can be attributed to CVD (14). The Colombian health system is divided in two different regimes, according to individuals' payment capacity. People able to contribute to the social security system and their beneficiaries are affiliated to the Contributory Regime, which is compulsory for formal employees and pensioners. The Subsidized Regime is financed by the State and covers the poor un-employed or informal-employed population. In Colombia, in the context of a market-oriented health system, cost-containment mechanisms imposed by health insurance companies often hamper timely access to health care, especially for those chronically ill, generating harmful consequences to people's lives (15).

In 2016 we carried out a cross-sectional survey in a low-income urban community in Medellin, aimed to estimate the prevalence of hypertension among the population aged 35 years or older and the magnitude and the determinants of the main gaps in hypertension care and control (Table 1).

**Table 1.** Main Gaps in hypertension care and control – definitions.

Gap	Numerator	Denominator	Remarks
Diagnosis	Number of unaware hypertensive individuals	The total surveyed population	Also calculated for hypertensives (nr. unaware /total hypertensives)
Pharmacological treatment	Number of aware hypertensive individuals who received prescription of antihypertensive medications but do not take any antihypertensive drug	Aware hypertensive individuals who received prescription of antihypertensive medications	
Follow-up	Number of aware hypertensive individuals who did not receive a follow-up consultation in the last year	Number of aware hypertensive individuals	

Control	Number of aware hypertensives with uncontrolled hypertension + Number of unaware hypertensives	The total hypertensive population (aware + unaware)	Also calculated in subgroup aware hypertensives
---------	--	---	---

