##### **A. Health services organization**

A.1. Hypertension screening: 1) all adults aged 35 years or older presenting to any health service (including clinical and support services) will be asked if they had their BP measured in the previous year. If not, they will be referred to a specific nursing hypertension service (“Healthy Hearts” service, see A.2 below) for a BP measurement, using a ticket stub for referral. 2) Doctors and nurses encountering presumptive hypertensive patients (individuals not reporting a previous diagnosis of hypertension but presenting BP higher than 140/90), will refer them to the “Healthy Hearts” service for confirmation of the diagnosis with serial BP measurement. 3) The entire health care flow for patients with a high BP measurement within health facilities will be standardized in order to guarantee continuity of care and correct diagnosis.

A.2. “Healthy Hearts” service: an auxiliary nursing station with extended opening hours and providing services such as BP measurement, global cardiovascular risk assessment and preventive counselling. It oversees serial self-measured BP monitoring within the health facility premises to exclude white coat hypertension, providing devices and patient education on self BP measurement. It will ensure retention and follow-up of all people with a high BP measurement at screening (at service level or in the community - see C.2 below) in order to guarantee that final diagnosis (hypertensive or not) is reached. It will refer to clinicians of the CVRP all newly diagnosed hypertensive patients. Through phone calls and/or SMS to patients and linkage with community agents, it will promote effective referral and manage non-attendance to follow-up CVRP consultations. It will administer periodical anonymous exit-questionnaires (annex 6) to hypertensive patients exiting from CVRP

consultations in order to assess effective BP measurement and the quality of pharmacological and non-pharmacological advice during medical consultations. Results will be transmitted to the cardiovascular risk team (see A.3.1 below).

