6. High calculated cardiovascular risk	Hypertensive patients with calculated cardiovascular disease risk $\geq 20\%$ in 10 years and systolic blood pressure (BP) $\geq 140/90$ mm Hg at last BP measurement during the last year.	Number of hypertensive patients enrolled in the CVRP	Billing and electronic clinical records	Pharmacological treatment (yes, no), sex, age	Biannual
7. Prevalence of controlled	Hypertensive patients with documented	Number of hypertensive patients	Billing and electronic clinical	Pharmacological treatment (yes,	Biannual

hypertension	systolic BP <140 mm Hg and diastolic BP <90 mm Hg in at the most recent BP measurement during the last year.	enrolled in the CVRP	records	no), sex, age	
8. Prevalence of controlled hypertension 6 months after enrolment in the CVRP	Hypertensive patients who started treatment 6 months before the reporting trimester and have systolic BP <140 mm Hg and diastolic BP <90 mm Hg at follow-up visit during the reporting trimester	Number of hypertensive patients enrolled in the CVRP who started treatment 6 months before the reporting trimester	Electronic clinical records	Sex, age, pharmacological treatment (yes, no), non-pharmacological treatment (yes, no)	Quarterly
9. Uncontrolled hypertension in patients with cardiovascular disease, renal disease or diabetes	Hypertensive patients diagnosed $\geq 6$ months before the start of the reporting period, and cardiovascular disease, renal disease, or diabetes mellitus, who had systolic BP $\geq 140$ mm Hg or diastolic BP $\geq 90$ mm Hg at the most recent BP measurement during the last	Number of hypertensive patients enrolled in the CVRP $\geq 6$ months before the start of the reporting period	Electronic clinical records	Pharmacological treatment (yes, no), sex, age	Quarterly

	year				
10. Uncontrolled hypertension 2	Hypertensive patients diagnosed $\geq 6$ months before the start of the reporting period who had systolic BP $\geq 160$ mm Hg or diastolic BP $\geq 100$ mm Hg at the most recent BP measurement during the last year	Number of hypertensive patients enrolled in the CVRP $\geq 6$ months before the start of the reporting period	Electronic clinical records	Pharmacological treatment (yes, no), sex, age	Quarterly

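### A blood pressure of exactly 140 or 90 is not high in an undiagnosed person but is uncontrolled in a diagnosed one; the effect on the trial is small

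*Combined protocol and SAP*

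**What the plan says.** Section 4.1.4 makes an undiagnosed person hypertensive, and by the same wording presumptive hypertensive, when "without previous diagnosis but presenting an average blood pressure (BP) measurement higher than 140/90 mmHg". A diagnosed person is controlled given "self-report of previously diagnosed hypertension and an average BP less than 140/90 mm Hg for patients between 35 and 59 years old or diabetics", with a limit of "150/90 mm Hg for patients aged 60 years or older".

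Table 1 (section 1.2) adds the two groups in the numerator of the control gap: "Number of aware hypertensives with uncontrolled hypertension + Number of unaware hypertensives". The denominator is all hypertensives, aware and unaware.

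In the intervention (section 4.2.1), A.1 item 2 has doctors and nurses refer presumptive hypertensives for serial measurement. They are described as "individuals not reporting a previous diagnosis of hypertension but presenting BP higher than 140/90". Item 1 is separate: it refers adults with no blood pressure reading in the past year, whatever their value.

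In Table 4A, indicators 17 and 20 and the denominator of indicator 18 count an average of at least 140 systolic or at least 90 diastolic as high. Indicators 15, 16 and 39 refer to high BP without giving a number.

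**The concern.** The strict operator for undiagnosed people and the strict operator for control point in opposite directions, so a value exactly on the limit falls on different sides according to diagnosis status. Both rules feed one main outcome. A person at such a value is outside the control gap while undiagnosed, and enters its numerator and denominator on being diagnosed, with no change in blood pressure.

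The same mismatch appears in the care pathway. A reading of exactly 140/90 need not trigger referral under A.1 item 2, although a serial average of 140/90 is high under indicator 17. At stake are who is counted, who is referred, and whether two analysts would report the same prevalence and gaps.

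**Working it through.** **1. Rules side by side (literal reading)**

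| Average BP | Undiagnosed | Diagnosed |
|---|---|---|
| 138/90, any age | not a case; outside the gap | uncontrolled; numerator and denominator |
| 140/85, age 35-59 or diabetic | not a case; outside the gap | uncontrolled; numerator and denominator |
| 140/85, age 60 or older, not diabetic | not a case; outside the gap | controlled; denominator only |

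Indicators 17, 18 (denominator) and 20 would call all three readings high.

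**2. The plan's own sample size.** Section 4.1.2 states that "a sample of 280 hypertensive individuals 35 years or older is required to estimate a 10% difference in the magnitude of the control gap", with a gap of 45%, power 0.75 and alpha 0.10. Comparing 45% with 35%, two-sided with continuity correction, gives 278 per commune, which reproduces the stated 280. Also 280/0.40 = 700, and 700 × 1.5 × 1.1 = 1,155 (stated 1,150). This point leaves those figures unchanged.

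**3. Starting levels**, from the 2016 survey in section 1.2 (two-commune baseline results are not given):
- aware: 0.434 × 0.633 = 27.5% of those surveyed, so undiagnosed = 72.5%;
- unaware hypertensive: 0.434 × 0.367 = 15.9% of those surveyed, or 22.0% of the undiagnosed;
- control gap: (0.41 × 27.5 + 15.9)/43.4 = 62.7%.

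**4. Share on the boundary (assumed model).** The documents give no blood pressure distribution and no number of readings per average. The model for undiagnosed people is bivariate normal with integer readings, correlation 0.65, and single-reading SDs (SBP/DBP) of 14/9, 16/10 or 18/11, including a within-person part of 6/4. Means are set so that 22.0% exceed 140 systolic or 90 diastolic. Averaging two or three readings, 0.52-1.12% of those surveyed are exactly on a limit and above neither. With 1,150 × 0.9 = 1,035 respondents per commune, that is about 5-12 people.

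**5. Effect on levels.** Let x be the boundary share of those surveyed, p the prevalence and g the control gap. Adding x to the unaware raises the gap by x(1 − g)/(p + x).
- 2016 gap, p = 0.434: x = 0.0052 gives 0.0052 × 0.373/0.439 = 0.4 points; x = 0.0112 gives 0.0112 × 0.373/0.445 = 0.9 points.
- Planning gap of 45%, x = 0.0112: 0.0112 × 0.55/0.445 = 1.4 points at p = 0.434, and 0.0112 × 0.55/0.411 = 1.5 points at p = 0.40.
- Prevalence moves from 43.4% to 43.9-44.5%.

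Digit preference enlarges this. With SDs 16/10 and two readings, x is 0.99%. If 20% or 40% of readings are rounded to tens (assumed), x becomes 1.4% or 2.7%, and the 2016 gap rises by 1.2 or 2.2 points.

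**6. Effect on the difference-in-differences.** Illustration: a true effect of 10 points, with the intervention commune's unaware share falling from 36.7% to 30% and the rest of the change coming from better control; the control commune does not change. The boundary share of undiagnosed people is the same in all four surveys. At 1%, 3% and 5% of undiagnosed people (0.7%, 2.2% and 3.6% of those surveyed at baseline), the estimate moves by 0.1, 0.4 and 0.6 points. For scale, with 280 effective hypertensives per commune per survey, the standard error is √(4 × 0.45 × 0.55/280) = 5.9 points.

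**7. Effect on referral.** On one unrounded reading, 9-12% of undiagnosed people at or above 140 or 90 fail the strict rule. The inclusive rule would therefore refer about 10-14% more than the strict one (0.089/0.911 to 0.121/0.879). This models the general undiagnosed population, not clinic attenders.

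**The case against.** The strongest reply is that this is editorial. The endline is tied to the baseline methodology, whose protocol is not supplied. A.3.2 promises a standardised diagnostic algorithm, and section 4.2 a field manual. A.1 item 3, A.2 and C.2 speak of high readings or positive screening without an operator. The code in use may already be consistent. That stands as a limit: the finding concerns the stated wording. It does not remove the inconsistency, because 4.1.4 and A.1 item 2 do state an operator and nothing supplied overrides it. It is also fair that indicators 17, 18 and 20 classify serial averages, a later stage than the item 2 reading.

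A reader might infer more than the documents support:

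- **That undiagnosed people are referred only above 140/90.** Item 1 refers regardless of the value; only item 2 carries the strict limit.
- **That indicators 6-9 and 12 also conflict with 4.1.4.** They cover patients in care and agree with the control rule for ages 35-59 and diabetics, so they add no conflict there.
- **That the 150 limit at age 60 or older is part of the fault.** It is a treatment target and need not mirror the case threshold.
- **That 0.9 points is a ceiling.** It depends on the 2016 gap and on readings without digit preference.
- **That the effect estimate is biased.** The same methodology is planned for both surveys, and nothing in the documents suggests that boundary values differ between communes.

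**Conclusion.** The concern holds as a minor inconsistency in the stated rules. The control gap treats an identical boundary reading differently by diagnosis status, and A.1 item 2 can miss people whom the trial's diagnostic indicators would count as high.

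The change in the reported control-gap level is about 0.4-0.9 points at the 2016 gap, up to 1.4-1.5 points at the planning gap, and more with digit preference. The difference-in-differences moves by well under 1 point if the boundary share is equal across communes and surveys. These sizes rest on the assumed distributions, on two or three averaged readings, and on reading 140/90 as either limit being exceeded, which 4.1.4 does not spell out. No bias, net direction or changed conclusion follows.

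**What to change.** In 4.1.4 and A.1 item 2, define a case and a referral as SBP ≥140 or DBP ≥90. Use the same cut-off for high BP in indicators 15, 16 and 39. Write controlled as SBP <140 and DBP <90, keeping SBP <150 for non-diabetics aged 60 or older. Apply identical code to the stored baseline and endline values in both communes. If the baseline survey already used one operator, state it and keep it for both surveys.

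The cost is about a line in each place, plus a rerun of the baseline classification if individual values are stored. There are three downsides:
- somewhat more referrals for serial measurement;
- a baseline prevalence that may rise by about one point from any figure already reported, or more with digit preference;
- in non-diabetics aged 60 or older, a difference between case and control limits that widens by one value (systolic 140). In the model, 0.22-0.59% of those surveyed are at exactly 140 systolic with diastolic below 90. If 35% of them are in this group (assumed), that is 0.1-0.2% of those surveyed.
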